15.2 Sample Size Justification for Vaccine Comparison

The primary focus of this trial will be to assess the worthiness of pp65-LAMP mRNA DC vaccine for further investigation by comparing overall survival (OS) between the active treatment group (Arms 1 and 2 combined) and the control group (Arm 3). Because this test for efficacy will be made within the framework of a phase II trial, we have constrained sample size requirements to yield adequate power to detect a clinically relevant improvement in OS at the expense of the false positive rate (α -level or Type I error rate). Adopting guidelines proposed by Ratain and Sargent (2009) and Rubinstein et al (2005), our proposed sample size of $40 + 40 = 80$ patients in the treatment group and 40 patients in the control group will allow detection of a clinically relevant improvement in the median OS time of the treatment group with 90% power at a one-sided α -level of 0.2.

In determining the effect size that can be detected by our proposed sample size, we considered using as a control reference level the median OS estimate of 14.6 months (95% CI: 13.2 to 16.8) reported by Stupp et al (2005) for patients receiving radiotherapy plus TMZ (RT+TMZ) for newly-diagnosed GBM (40% of patients in the Stupp trial were grossly resected). In the Stupp trial, randomization occurred prior to any post-surgical treatment, and the timing of randomization in our study will be similar. However, in our study, patients will not begin to experience potential differential effects due to treatment until after their first vaccination, which will occur approximately 15 weeks after randomization. To determine an appropriate control reference level for median OS for an index day 15 weeks after randomization, we carefully transferred the coordinates of multiple points along the Stupp RT+TMZ OS curve into a statistical software package. We determined that median OS relative to a starting time 15 weeks after the Stupp index day would be 13.8 months. We also observed that RT+TMZ OS times appeared to approximately follow a Weibull distribution with a shape parameter = 1.20, indicating a slightly accelerating baseline hazard function. Upon examining in a similar manner the RT+TMZ OS curve reported in the paper by Gilbert et al (2013), we also observed approximately Weibull-distributed OS times with shape parameter = 1.16.

We therefore used 13.8 months as the median OS reference level for our control group and assumed Weibull-distributed OS times with a common shape parameter value for both the treatment and control groups. This is equivalent to assuming Weibull-distributed OS times with proportional hazards between the treatment and control groups.

Using methods adapted from Wu and Xiong (2014), we calculated improvement in median OS (or equivalently, the largest treatment vs. control hazard ratio less than 1) that could be detected by a log rank test with 90% power at 1-sided $\alpha=0.20$, for selected Weibull shape parameter values ranging from 1.00 (equivalent to exponential survival with constant hazard) to 1.25 (accelerating hazard). We assumed 120 patients would be randomized and proceed to vaccination at a uniform rate over a 3-year accrual period. These patients would then be followed after the end of accrual for one additional year. As summarized in the following table, 77 deaths (expected by follow-up

times ranging from 45.1 to 48.9 months, depending on the degree of hazard acceleration assumed) will allow a treatment vs. control hazard ratio of 0.6 to be detected with sufficient power. Equivalently, improvement in median OS ranging from 7.0 to 9.2 months (again, depending on the degree of hazard acceleration assumed) can be detected with sufficient power.

Improvement in median overall survival (Surv50) that can be detected at 90% power and a one-sided alpha-level of 0.20, for possible Weibull shape parameters characterizing the degree of hazard acceleration:

Weibull			Detectable effect at 90% power, 1-tail alpha=0.20		
TRT:	Shape	Baseline hazard function trend	Expected # of months to observe 77 deaths	Surv50 (months)	Hazard ratio
CTL N	parameter				
80:40	1.00	Constant (exponential survival)	48.9	+ 9.2	0.60
80:40	1.16	Accelerating (Gilbert et al)	46.3	+ 7.6	0.60
80:40	1.20	Accelerating (Stupp et al)	45.7	+ 7.3	0.60
80:40	1.25	Accelerating	45.1	+ 7.0	0.60

15.3 Analytic Methods

15.3.1 Primary Objective and Secondary Clinical Objectives

We will use Kaplan-Meier survival curves and the log rank test to characterize and compare PFS and OS in patients who received pp65-LAMP mRNA DC vaccine (Arms 1 and 2) and in control patients (Arm 3). PFS is defined as the time between first vaccination and first documentation of either disease progression/recurrence, or death without prior progression/recurrence. Patients remaining alive without disease progression will have PFS censored at last follow-up. OS will be defined as the time between first vaccination and death, and will be censored at the last follow-up if death has not occurred. We will also perform a stratified analysis incorporating the three stratification variables (age, RPA class, and CMV sero-status) using Cox proportional hazards regression. The index day for all of our primary comparisons will be the time of the first vaccination. Because patients who fail to proceed to the first vaccination because of GBM recurrence or for other reasons cannot experience differential effects due to treatment arm membership, we will not perform an intent-to-treat analysis that includes these patients. We will perform an intent-to-treat analysis of OS and PFS that includes patients who begin the vaccination sequence but who do not receive at least three vaccinations because of recurrence or other reasons. OS and PFS times for adequately vaccinated patients who are lost to follow-up will be considered right-censored at the time of loss and will be included in all of our survival comparisons.

All subjects who receive at least one dose of DC vaccine will be considered evaluable for purposes of safety and toxicity.

All subjects who complete chemoRT and receive dose-intense adjuvant TMZ and at least 3 DC vaccines will be considered evaluable for purposes of the primary and secondary endpoints.

The impact of pp65-LAMP mRNA DC vaccine on PFS and OS in patients with gross total resection will also be explored using the log rank test and Kaplan-Meier curves, although our trial design may not necessarily achieve sufficient power to detect a clinically meaningful effect within this patient subgroup.

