Appendix B, C and D are provided as guidelines for dose modifications and chemo management.

Patients age 70 and above, will receive standard dose Temozolomide at 150-200 mg/m²/day for 5 consecutive days of a 35 (+/7) days cycle. For these subjects, one dose reduction to 100 mg/m²/day for 5 days will be allowed based on AE on previous cycle.

In the event that chemo adjuvant cycle is delayed past the timeframe provided in Appendix C and D, the treatment with Temozolomide may resume when toxicity has resolved (or returned within treatment limits) if patient has not experienced tumor progression at the discretion of the PI in consultation with the treating physician, if the PI believes that it is safe to continue therapy and that the patient may benefit from additional chemo cycles. Study vaccines will be given at day 22-24 of each cycle when chemo is restarted.

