10 STUDY REQUIREMENTS

10.1 Enrollment

- Signed informed consent.
- History, physical & neurological exam
- MMSE for subject \geq 50 years.
- Histopathology report confirming GBM (WHO Grade IV Glioma) and molecular diagnostics.
If molecular testing were not performed at time of diagnosis, promoter hypermethylation of the *O6*-methylguanine-methyl-transferase (*MGMT*) gene, and the mutation status of the *IDH1* and *IDH2* genes will be obtained for study data analysis.
- Preoperative MRI (or CT).
- Postoperative MRI (or CT) within 28 days of study enrollment. If the postoperative MRI is older than 28 days, a new MRI will be obtained prior to patient randomization. The new MRI will serve as baseline MRI.
- Karnofsky Performance Status.
- CBC with differential and CD4+/CD8+ T cell ratio.
- Infectious disease testing to include: HIV, Hepatitis B, Hepatitis C and CMV.
- For females of child-bearing potential, β -HCG serum pregnancy test.
- Pathology slides (if available) consisting of 1 hematoxylin and eosin (H&E) and 19 unstained slides, from all prior resections, prepared on Fischer Plus glass or Histostix coated slides.

- Confirm eligibility.

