11.1 General Methodology for Determining Tumor Measurements

[figure not shown]
Newly diagnosed GBM patients will initially undergo a pre-entry MRI scan for initial diagnosis prior to entry in the study and prior to therapy. The post-operative scan will determine residual enhancing disease which may be used as a covariate in survival analyses. Patients will then start on standard therapy, Temozolomide with concurrent radiation therapy (RT). **The Post-RT scan will be required and used as the baseline scan** for which response will be determined. Following the first cycles of adjuvant therapy, patients will receive additional required MRI scans.

All radiographic responses will be based on MRI scans of the brain obtained with and without contrast. Tumor size will be based on the product of the maximal diameters in 2 different planes. Response will be assessed as a percentage change in tumor size from baseline. Tumor measurements in the follow-up scans will be compared to those of the post-RT scan to document response.

Definition of Measurable Disease, Non-Measurable Disease, and Target Lesions

Measurable disease should be defined as contrast enhancing lesions with a minimum size of **both** perpendicular measurements greater than or equal to 10mm (if the largest diameter is greater than 10mm but the perpendicular diameter is less than 10mm, this would constitute non-measurable disease). Up to a total of five target measurable lesions should be defined and ranked from largest to smallest.

Algorithm for identifying measurable and target lesions:

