15 STATISTICAL METHODS AND DATA ANALYSIS

15.1 Study Design Overview

The primary goal of this randomized phase II study is to determine whether the addition of pp65-LAMP mRNA DC vaccination in adult patients with newly-diagnosed GBM receiving dose-intensified TMZ will be a treatment worthy of investigation in a large phase III study. A secondary

objective will be examination of the immunologic responses induced by full-length vs short LAMP sequences.

Although this randomized phase II study is comparative, it will not be definitive as the assessment will be conducted with a large false-positive rate. We have included a concurrently followed control arm in the trial design in lieu of a historical control group to ensure that appropriate comparisons can be made without concern that the patients receiving standard treatment differ in prognostic factors or standards of care (Rubinstein, 2009; Ratain and Sargent, 2009; Rubinstein et al., 2005).

We will randomize eligible patients, after enrollment, to one of 3 study arms in which they will receive 21-day TMZ concurrently with one of the following treatments:

Arm #	Vaccine	Skin Preparation
1	pp65-shLAMP mRNA DCs with GM-CSF	Tetanus
2	pp65-fLAMP mRNA DCs with GM-CSF	Tetanus
3	PBMCs	Saline

Randomization will be stratified by:

- Age 69 years old and younger; or 70 years old and older
- RPA Class (III, IV, or V)
- CMV seronegative or seropositive

We will use a permuted block randomization scheme with a 1:1:1 study arm allocation ratio and a block size of 6 within each stratum.

Adapted RPA Stages For Malignant Gliomas (Survival With Concurrent Temozolomide and Radiation Therapy vs Radiation Therapy alone)				
Stage	Characteristics	Median OS	2-year OS	p-value vs. control
III	Age <50, PS 0	21 vs. 15 mo	43% vs. 20%	p<0.0001
IV	Age <50, PS 1-2 Age >=50, Surgery, MMSE >=27	16 vs. 13 mo	28% vs. 11%	p<0.01
V	Age >=50 and either Biopsy only or MMSE <27	10 vs. 9 mo	17% vs. 6%	p=0.05

Approximately 200 patients will be enrolled in the study, randomized and receive “standard-of-care” radiotherapy concurrent with TMZ under the assumption that approximately 120 patients will be vaccinated according to treatment arm.

A Data Sharing Agreement has been established with Immunomic Therapeutics, Inc. and the University of Florida. A Limited Data Set will be sent to evaluate immunogenicity and clinical efficacy of the vaccine products used within this clinical trial (for patients treated at the UF site

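### Cheap improvement: the OS decision test is an unadjusted log-rank; one additive Cox test with the randomisation factors and MGMT would protect the go/no-go against chance MGMT imbalance

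*Combined protocol and SAP*

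**What the plan says.** - **Section 15.2** bases the sample size on an effect "that could be detected by a log rank test with 90% power at 1-sided" alpha 0.20: HR 0.60, 77 deaths, 80 vaccine and 40 control patients.
- **Section 15.3.1** gives the test: "We will use Kaplan-Meier survival curves and the log rank test to characterize and compare PFS and OS". The comparison is Arms 1 and 2 together against Arm 3, with no covariates or strata. It then adds: "We will also perform a stratified analysis incorporating the three stratification variables (age, RPA class, and CMV sero-status) using Cox proportional hazards regression". It does not say whether this second result can alter the decision, or whether the three factors enter as strata (separate baseline hazards) or as covariates.
- **Section 15.1** stratifies the randomisation by age group, RPA class and CMV serostatus: "We will use a permuted block randomization scheme with a 1:1:1 study arm allocation ratio and a block size of 6 within each stratum".
- **Section 10.1** requires MGMT promoter and IDH status where not already tested; the results for these "genes will be obtained for study data analysis". The Summary of Protocol Changes (version 20230509) calls both a requisite for analysing glioblastoma studies. Section 15 names neither. Section 15.3.2 mentions only unspecified potential confounders, and only for the immune-response models.
- **Section 11.1** speaks of "residual enhancing disease which may be used as a covariate in survival analyses"; section 15.3.1 does not take this up.
- **Age:** section 15.3.1 says that patients who complete chemoradiation and "receive dose-intense adjuvant TMZ and at least 3 DC vaccines will be considered evaluable for purposes of the primary and secondary endpoints", while section 9.5 says "Patients age 70 and above, will receive standard dose Temozolomide". Age group could therefore be constant in the evaluable set.

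**The concern.** The phase III go/no-go rests on one comparison with 40 controls. RPA class is strongly prognostic by the plan's own table. The plan also treats MGMT as needed for analysis, yet neither the randomisation nor the decision test deals with it. If the methylated share happens to differ between the groups, the log-rank credits the difference to the vaccine or charges it against the vaccine. The analysed patients are also selected after randomisation (about 200 randomised, about 120 vaccinated), so blocking does not guarantee balance even on the stratified factors. The data needed to adjust are already being collected.

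**Working it through.** **1. The plan's own figure.** Inputs from section 15.2: HR 0.60, one-sided 0.20 (z = 0.842), 90% power (z = 1.282), 2:1 allocation (2/3 × 1/3 = 2/9). By Schoenfeld's formula:
- deaths = (0.842 + 1.282)² / [(2/9) × (ln 0.6)²] = 77.7
- power at 77 deaths = Φ(√(77 × 2/9) × 0.511 − 0.842) = Φ(1.27) = 0.898

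The stated 77 deaths and 90% reproduce.

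**2. Prognostic strength of RPA class.** The medians in section 15.1 are 21, 16 and 10 months. At Weibull shape 1.2 (section 15.2), the HR for IV vs III is (21/16)^1.2 = 1.39, and for V vs III (21/10)^1.2 = 2.44. The second overstates the spread here: class V in that table includes biopsy-only patients, whom inclusion criterion 4 excludes.

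**3. How often MGMT is unbalanced.** The documents give no prevalence; 40% methylated is assumed. The SD of the difference in methylated share, 80 vs 40 patients, is √(0.4 × 0.6 × (1/80 + 1/40)) = 0.095. A difference of at least 10 points then has probability about 0.29 (some 15% in each direction), and of at least 15 points about 0.11.

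**4. Effect on the log-rank, by hand.** Given at least 10 points in one direction, the mean imbalance is about 0.149. The standard error of the log HR is 1/√(77 × 2/9) = 0.242. The z shift is 0.149 × |ln(MGMT HR)| / 0.242 = 0.22, 0.31 and 0.43 at MGMT HR 0.7, 0.6 and 0.5.
- False-go, imbalance favouring vaccine: Φ(−0.842 + shift) = 0.27, 0.30, 0.34.
- Power, imbalance against vaccine: Φ(1.27 − shift) = 0.85, 0.83, 0.80.

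**5. Simulation.** 200 patients in permuted blocks of 6 within 12 strata, a random 120 vaccinated, Weibull shape 1.2, 36-month accrual, analysis at the 77th death, RPA medians as in section 15.1. Assumed: RPA mix 15/55/30%; age 70+ in 22% of classes IV and V, HR 1.2; CMV positive 33%, no effect on survival; MGMT methylated 40%. The adjusted test is additive Cox on RPA class, CMV, age group and MGMT.

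Trials with at least 10 points of MGMT imbalance (12,000 trials per setting, about 1,660 to 1,840 in each direction, simulation error about 1 point; power at HR 0.60 within covariate levels):

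| MGMT HR | False-go: log-rank | adjusted | adjusted, 20% MGMT unknown | Power: log-rank | adjusted | adjusted, 20% MGMT unknown |
|---|---|---|---|---|---|---|
| 0.7 | 0.25 | 0.21 | 0.22 | 0.85 | 0.89 | 0.88 |
| 0.6 | 0.31 | 0.22 | 0.25 | 0.82 | 0.91 | 0.89 |
| 0.5 | 0.33 | 0.21 | 0.24 | 0.78 | 0.90 | 0.88 |

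A separate run (9,000 trials per setting) gave, at MGMT HR 0.7 and 0.5, false-go 0.25 and 0.33 (adjusted 0.20 and 0.22), and power 0.85 and 0.74 (adjusted 0.90 and 0.89).

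Average over all trials, size-corrected power at HR 0.60 within covariate levels (8,000 trials per setting, simulation error 0.3 to 0.4 point):

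| MGMT HR | Log-rank | Strata over all cells | Additive, three factors | Additive + MGMT | Additive + MGMT, 20% unknown |
|---|---|---|---|---|---|
| 1.0 | 0.882 | 0.870 | 0.895 | 0.893 | 0.888 |
| 0.7 | 0.892 | 0.876 | 0.896 | 0.898 | 0.896 |
| 0.6 | 0.880 | 0.863 | 0.884 | 0.895 | 0.888 |
| 0.5 | 0.865 | 0.853 | 0.866 | 0.888 | 0.881 |

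With blocks applied directly to the 120, the gain from additive + MGMT ran from −0.2 (MGMT HR 1.0) to +2.4 points (0.5). A variant with RPA mix 20/55/25% and age HR 1.3 gave +1.1 and +2.8 points at MGMT HR 0.7 and 0.5. The three factors alone add about 1 point or less (one cell shows 1.3). Strata over all cells lose 0.6 to 1.7 points: of 2 × 3 × 2 = 12 cells, two are empty because class III requires age under 50, which leaves 77/10, or about 8 deaths per cell.

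**6. Level.** With no vaccine effect, the nominal 0.20 cut-off rejects in 0.193 to 0.209 of trials for the log-rank and 0.208 to 0.221 for the adjusted test. With a re-randomisation cut-off and 20% of MGMT unknown, power was 0.877 against 0.888 for the log-rank (no MGMT effect), and 0.870 against 0.860 (MGMT HR 0.5).

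**The case against.** The log-rank is a valid test, it matches the power calculation, and section 15.1 says openly that the trial is not definitive. At an unadjusted HR of 0.60, the effect actually planned for, it has simulated power of 0.899 to 0.918. Part of the shortfall in the second table arises because HR 0.60 within covariate levels corresponds to an unadjusted HR of 0.614 to 0.629. Chance imbalance is already averaged into the 0.20. The three factors add little, and section 15.3.1 already analyses them in a Cox model. MGMT prevalence and effect come from outside the documents. A late change of decision test in a single-blind trial, where section 9.3 has site personnel randomise, carries a credibility cost.

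All of that stands, and it makes this an improvement rather than a correction. It does not remove the conditional result: once a particular trial has a material MGMT imbalance, the log-rank's long-run 0.20 no longer describes that trial's risk, and a collected covariate would reduce the problem.

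A reader might go further and infer that the stated power is wrong, that the plan ignores its stratification factors altogether, or that adjustment fully restores 0.20 and 0.90. The documents and figures support none of these. The 77 deaths reproduce, the supplementary Cox analysis exists, and with 20% of MGMT unknown the adjusted false-go rate is still 0.22 to 0.25. Nor do the documents show that outcomes have been compared by arm; they record only that the interim analysis was dropped.

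**Conclusion.** The point holds as an inexpensive improvement. On average the gain is about 0 to 2.5 size-corrected points at 40% methylated and MGMT HR 1.0 to 0.5, nearly all of it from MGMT when MGMT matters, with up to about 1 point lost if MGMT has no effect and 20% is unknown. The case rests on the roughly 30% of trials with an imbalance of 10 points or more. There, at MGMT HR 0.7 to 0.5, the log-rank moves to a false-go rate of about 0.25 to 0.33 or a power of about 0.85 to 0.75, while the adjusted test stays near its targets (about 0.22 to 0.25 and 0.88 with 20% unknown). These sizes depend on the assumed MGMT prevalence and effect, and on random attrition between randomisation and vaccination. Whatever is decided about the main test, the plan should say which result governs, how the three factors enter the Cox model, and where MGMT is used.

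**What to change.** Before any comparison by arm, amend section 15.3.1 as follows.

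- **Decision test.** For OS, and likewise for PFS, use the one-sided 0.20 treatment term from one Cox model with additive covariates: RPA class, CMV serostatus, age group (dropped if constant in the analysed set) and MGMT (methylated, unmethylated, unknown). Do not use strata over all age × RPA × CMV cells. The count is 1 treatment + 2 RPA + 1 CMV + 1 age + 2 MGMT = 7 parameters, or 77/7 = 11 deaths each.
- **Sensitivity analysis.** Keep the unadjusted log-rank, labelled as unable to change the decision.
- **Supportive model.** Name residual enhancing disease and IDH in one supportive model only.
- **Cut-off.** State that the nominal cut-off rejects in about 0.20 to 0.22 of trials under no effect. Use a re-randomisation cut-off only if it follows the stratification in force when each patient was randomised. The Summary of Protocol Changes (versions 20170801 and 20171106) indicates that CMV and age stratification were added in 2017, after enrolment had begun.
- **Fallback.** If nobody can attest that the amendment was written without sight of outcomes by arm, keep the log-rank as the decision test and name the additive Cox model with MGMT as the supportive analysis. The attestation must come from whoever writes the model.

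The cost is one amendment and no new data collection. The downsides are its lateness, some missing MGMT results (the requirement dates from version 20230509 and slides are collected only if available), a slightly raised error rate at the nominal cut-off, and little or no gain if MGMT has little effect.

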Patients will be imaged bimonthly during TMZ cycles and every 3 months after the 12th TMZ cycle (or 1 year post surgery if TMZ discontinued prior to 12 cycles) without receiving any other prescribed antitumor therapy unless progression occurs.

The primary measure of response will be by serial measures of the product of the two largest cross-sectional diameters. The modified RANO criteria (Ellingson, Wen, Cloughesy 2017) will be used for assessment of pseudoprogression, progression or response.

Tumor progression should be documented histologically, unless there are clinical contraindications, to exclude inflammatory responses presenting as radiographic or clinical changes, which could indicate potentially toxic or therapeutic responses and not tumor progression. As this is not a research procedure, consent for biopsy will be obtained separately. If tissue is obtained, it will be used to confirm tumor progression histologically and evaluate cellular infiltration and CMV antigen expression at the tumor site.

If histopathology confirms treatment effect vs tumor progression, the patient may resume study treatment at the discretion of the PI in consultation with the treating physician, if the PI believes that it is safe to continue therapy and that the patient may benefit from the ongoing treatment regimen as described in section 11.11 Confirmation of Tumor Progression by Histopathology.

Patients will be followed until death due to any cause. MRI and clinical evaluation for assessment of disease progression will be conducted bi-monthly for the first 12 months and then every 3 months thereafter.

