10.6 Concomitant Medication

The following medications will be recorded with start date, stop date, and indication:

- Steroids
- Anticonvulsants
- Bevacizumab
- Any medication used in the treatment of a study drug related AE/SAE
- Any medication deemed to possibly be interactive with study drug by PI or designee.

Concomitant medication will be recorded at the time of vaccine #1 and continue until 30 days after the last dose of study drug and at leukapheresis time point.

Use of bevacizumab:

Bevacizumab is not a study drug on this trial. However, for patients who develop radiation necrosis symptoms, a short trial of bevacizumab can be considered at the discretion of the PI in consultation with the treating physician, if the PI believes that the patient may benefit from the treatment. Dose and frequency of bevacizumab treatment will be at the discretion of the investigator in keeping with standard of practice (bevacizumab 5-10 mg/kg every 2-3 weeks) for up to 3 months treatment.

NOTE: Bevacizumab is to be used for participants who develop symptomatic radiation necrosis, and is not intended to be used to treat the underlying tumor.

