11 RESPONSE EVALUATION

The modified RANO provides clinical guidelines for continuing therapy **beyond** suspected radiographic progression if the treating physician believes there may be a therapeutic benefit and provides criteria for defining progression and early drug failure while also allowing for the possibility of pseudoprogression (PsP) and pseudoresponse (PsR). An update to the RANO criteria proposes strategies to establish a general framework for response assessment in neuro-oncology that is agnostic to the mechanism of action of the particular therapy (anti-angiogenic, immunotherapy...) to address the challenges associated with interpretation of radiographic changes in patients with glioblastoma in clinical trials. The modified RANO proposes to **use the post-radiation time point as the baseline** for response evaluation and to consider only objectively defined, measurable enhancing disease in the definition of response and progression (i.e. exclusion of qualitative assessed T2/FLAIR changes)

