2. In the case where the baseline or best response demonstrates no measurable enhancing disease (visible or not visible), then any new *measurable* ($>10\text{mm} \times 10\text{mm}$) enhancing lesions are considered PD *after* confirmed by a subsequent scan ≥ 4 weeks exhibiting $\geq 25\%$ increase in sum of products of perpendicular diameters of enhancing lesions relative to the scan first illustrating new measurable disease. The first scan exhibiting new measurable disease is noted as “preliminary PD.” If the second scan at least 4 weeks later exhibits a subsequent $\geq 25\%$ increase in sum of products of perpendicular diameters of enhancing lesions relative to the “preliminary PD” scan it is considered “confirmed PD” and the patient should discontinue therapy. If the second scan at least 4 weeks later exhibits SD, CR, PR, or becomes non-measurable, this scan showing “preliminary PD” is noted as “pseudoprogression”, PsP, and the patient should continue on therapy until a second increase in tumor size relative to the “preliminary PD”, or PsP, scan is observed. Note that any new *measurable* ($>10\text{mm} \times 10\text{mm}$) enhancing lesions on the subsequent scan following the preliminary PD scan should *not* be immediately considered confirmed PD, but instead should be added to the sum of bidimensional products or total volume representing the entire enhancing tumor burden.
3. Clear clinical deterioration not attributable to other causes apart from tumor (e.g. seizures, medication adverse effects, therapy complications, stroke, infection) or attributable to changes in steroid dose.
4. Failure to return for evaluation as a result of death or deteriorating condition.

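### PFS is censored at last follow-up, not at the last tumour assessment, so patients who are alive and stable but no longer scanned count as progression-free

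*Combined protocol and SAP*

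**What the plan says.** Section 15.3.1 defines the endpoint: "PFS is defined as the time between first vaccination and first documentation of either disease progression/recurrence, or death without prior progression/recurrence". For the rest, "Patients remaining alive without disease progression will have PFS censored at last follow-up". OS is censored at last follow-up too. The term is not defined and is not tied to a scan. Adequately vaccinated patients who are lost "will be considered right-censored at the time of loss".

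Section 9.1 sets the length of follow-up: "Patients will be followed until death due to any cause". It adds that MRI and clinical evaluation for progression "will be conducted bi-monthly for the first 12 months and then every 3 months thereafter".

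Section 11.5 counts clear clinical deterioration as progressive disease, and also "Failure to return for evaluation as a result of death or deteriorating condition". Section 11.6 does the same for symptomatic deterioration without objective progression.

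On bevacizumab, section 10.6 says that for symptomatic radiation necrosis "a short trial of bevacizumab can be considered at the discretion of the PI", for up to 3 months. It is recorded with dates and indication, but only until 30 days after the last study drug. Section 11 bases radiographic progression on measurable enhancing disease ("exclusion of qualitative assessed T2/FLAIR changes"). The status table in 11.8 takes steroids into account but not bevacizumab. Section 15.3.1 has no PFS rule for missed scans, for bevacizumab, or for other anti-cancer therapy started before progression.

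**The concern.** Vital status and tumour status are observed by different means. Contact with the patient settles the first. The second needs an assessment, usually a scan. A single censoring date for both endpoints treats knowledge that a patient is alive as knowledge that the patient has not progressed.

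Two groups are affected once scans stop. Patients still alive are carried event-free to last follow-up. Patients who progress unseen and die later are carried event-free to the date of death. Both keep the PFS curve too high. If scans stop more often in one group, the comparison also shifts in that group's favour. PFS is the first secondary objective in 5.2.2, and the landmark models in 15.3.2 use it as well.

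**Working it through.** **Plan's own figure.** The documents give no event count, power or alpha for PFS. The nearest stated figure is the 77 deaths for OS in 15.2 (hazard ratio 0.60, 80:40, 90% power, one-sided alpha 0.20). The Schoenfeld formula gives (0.842 + 1.282)² / [(2/3)(1/3)(ln 0.60)²] = 77.7, and power with 77 deaths is 89.8%. The figure reproduces as a one-sided test at 0.20, and nothing below changes it. I use the same 0.20 for PFS, as an assumption.

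**Which patients the rule reaches.** Taking 15.3.1, 11.5 and 11.6 together:

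| Patient's situation | PFS status under the plan |
|---|---|
| Clear clinical or symptomatic deterioration | Event |
| Does not return because of decline or death | Event |
| Dies without documented progression | Event at death, however long since the last scan |
| Lost to follow-up | Censored at loss |
| Alive, in contact, not deteriorating, not scanned | Event-free to last follow-up |

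The last row is the problem. The third row is a smaller one when the gap before death is long.

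**Level of the PFS curve.** Assumed: Weibull progression times with shape 1.2, true median 7 or 10 months from first vaccination, median 8 months from progression to death, and scan stopping at 1 to 8 months in 10% or 20% of patients who stay in survival follow-up. Scans are every 2 months in year 1 and every 3 months after that (9.1, reading bi-monthly as every two months). True 12-month PFS is exp[−ln 2 × (12/median)^1.2], which is 0.266 at median 7 and 0.422 at median 10. Simulated Kaplan-Meier estimates under the rule as written:

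| True median | Scan loss | As written | True | Excess |
|---|---|---|---|---|
| 7 months | 10% | 0.298 | 0.266 | 0.032 |
| 7 months | 20% | 0.329 | 0.266 | 0.063 |
| 10 months | 10% | 0.450 | 0.422 | 0.028 |
| 10 months | 20% | 0.477 | 0.422 | 0.055 |

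Moving only the living patients' censoring to the last scan removes about half of the excess. In a separate run at median 7 and 10% loss, the estimate fell from 0.295 to 0.281, against 0.267 with no scan loss. Also censoring deaths that follow a long gap (over 6 months in the run) brings it to between 0.263 and 0.267. At 20% loss the two rules together give 0.258 (median 7) and 0.415 (median 10), slightly below the truth.

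**The comparison.** Assumed: 80:40, accrual over 36 months plus 12 months of follow-up as in 15.2, exponential PFS with median 6 or 9 months, median 7 months from progression to death, scans stopping at random in months 0 to 12, and no true effect. There were 1,000 runs per row, with Monte Carlo standard error about 0.013 to 0.015. The last-scan columns move living patients only. Ranges cover the two medians.

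| Scan loss, vaccine / control | Error, last follow-up | Hazard ratio | Error, last scan | Hazard ratio |
|---|---|---|---|---|
| 0% / 0% | 0.20–0.21 | 0.99–1.00 | 0.20–0.21 | 0.99–1.00 |
| 10% / 10% | 0.20–0.22 | 0.99–1.00 | 0.21–0.22 | 0.98–1.00 |
| 20% / 20% | 0.21 | 0.99 | 0.21 | 0.98–0.99 |
| 20% / 10% | 0.25–0.27 | 0.95–0.96 | 0.18–0.23 | 0.98–1.00 |
| 30% / 10% | 0.33–0.34 | 0.90–0.91 | 0.21–0.25 | 0.96–0.99 |

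With equal loss the two rules give the same error and median PFS differs by at most 0.4 months. With unequal loss the present rule favours the group that is scanned less.

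**The case against.** The strongest reply is that the protocol already catches most patients who stop being assessable. A reader might infer from the censoring sentence that every such patient counts as progression-free. The documents do not support that: decline, non-return through decline, and death are events, and lost patients are censored at loss. It is also too strong to say that progression can be seen only on scans, because clinical deterioration is a criterion in its own right.

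A second reply is that 9.1 schedules progression imaging with no stated end before death, so last follow-up could mean the last such evaluation. That reading is possible. But 15.3.1 uses the same words for OS, where the date last known alive is the natural meaning, and nothing in the text separates the two.

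Third, no scan-loss rate is documented. One might infer that loss will be heavier in the vaccine arms, because 13.1 ends study-related procedures after a dose-limiting toxicity. The text does not say that surveillance MRI stops; 10.4 describes it as part of routine clinic visits. The change summary for version 20201201 reports only 2 immunotherapy-associated events of Grade 3 or greater, with 132 patients enrolled. Imbalance is therefore a risk, not a finding. The plan also names no 12-month PFS endpoint, so the 3 to 6 points describe the curve and not the planned test.

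Fourth, bevacizumab. A reader might infer that unblinded staff use it to hold patients progression-free. The protocol says single-blinded without naming the blinded party, limits bevacizumab to symptomatic radiation necrosis and not the tumour, and records it. Section 11 also allows for pseudoresponse. Keeping these patients in the analysis is defensible, and censoring them may be informative because they are symptomatic. What stands is that the PFS analysis says nothing about them.

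**Conclusion.** The concern holds in a narrow form. The PFS censoring date in 15.3.1 should be the last adequate tumour assessment. As written, the rule credits progression-free time to patients who are alive, in contact and not deteriorating but no longer scanned.

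Under an assumed 10% to 20% scan loss, 12-month PFS is about 3 to 6 points too high. The log-rank comparison is nearly unaffected if loss is equal. It becomes too liberal if the vaccine arms lose more: one-sided error is 0.25 to 0.27 at 20% against 10%, and 0.33 to 0.34 at 30% against 10%. Loss rates, PFS medians and post-progression survival are all assumptions. The OS analysis and its 77 deaths do not change. The point is worth correcting because PFS is a named secondary objective and the correction is cheap.

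**What to change.** In 15.3.1:

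1. Censor PFS for patients without progression or death at the last adequate tumour assessment, or at first vaccination if there is none.
2. Censor a death that follows a long gap without scans, for example two or more missed scheduled assessments, at the last adequate assessment before the gap. Without this, about half of the overstatement remains.
3. Keep the present last-follow-up rule as a sensitivity analysis.
4. As a secondary sensitivity analysis only, report bevacizumab use by arm and repeat PFS censoring at the last scan before first bevacizumab. State that this censoring may be informative. Under 10.6 the dates are recorded only until 30 days after the last study drug, so later use would have to be retrieved or its absence declared.

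The cost is a few sentences in the plan, slightly earlier censoring, slightly fewer PFS events, and one or two extra analysis runs.
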